2.4.5.1 Analyses of hypoglycemia

All analyses of hypoglycemia events will be performed on the safety population, separately on events occurring during the 24-Weeks TEAE period (as defined in [Section 2.1.4](#)). The analyses planned to be done during the 24-Weeks TEAE period only (as defined in [Section 2.1.4.1](#)).

Patients with at least one hypoglycemia event

- Number and incidence of patients with at least one hypoglycemia event will be presented for any hypoglycemia and for each hypoglycemia ADA category, overall and by time of the day (as described in [Section 2.1.4.1](#)).
- For any hypoglycemia and for each hypoglycemia ADA category (except probable, pseudo), incidence of patients with at least one hypoglycemia will be compared, overall and by time of the day. Odds Ratio and its corresponding 95% CI of Virtual group over Traditional group for each hypoglycemic event will be estimated by a logistic regression model adjusted on randomization strata of screening HbA1c (<7.6%, ≥7.6%) and randomization strata of sites.
- Percentage (%) of patients with at least one severe hypoglycemia event will be summarized by symptom during 24 weeks TEAE period,

Number and rate of hypoglycemia event

- Number and rate of hypoglycemia event per patient-year will be summarized for any hypoglycemia and for each hypoglycemia ADA category (as described in [Section 2.1.4.1](#)), overall and by time of the day (as described in [Section 2.1.4.1](#)). Non classified hypoglycemia will be displayed.
- For any hypoglycemia and for each hypoglycemia ADA category (except probable, pseudo), the number of hypoglycemia events per patient-year will be compared, overall and by time of the day. For each hypoglycemic event, the rate ratio, and its corresponding 95% CI, of Virtual group over Traditional group will be estimated using an over-dispersed Poisson regression model adjusted on randomization strata of screening HbA1c (<7.6%, ≥7.6%) and randomization strata of sites.

For Hypoglycemic ADA categories, only the threshold hypoglycemia episodes with plasma glucose ≤70 mg/dL (3.9 mmol/L) will be analyzed.

Subgroups analyses

- The incidence of patients with at least one any hypoglycemia during the 24-week TEAE period, will also be presented by the following subgroups (defined below) and analyzed using a similar logistic regression model approach as presented previously, but adding the corresponding subgroup factor and study conduct approach arm-by-subgroup interaction factor. Odds ratio estimates and 95% CI will be provided in each subgroup category. The interaction study conduct approach arm-by-subgroup p-value will be provided for descriptive propose. When the subgroup considered is equal to one of the randomization strata or is part of one of the adjustment factor, this randomization stratum/adjustment factor is removed from the model. If the logistic regression model does not converge (eg, due to sparse data) some of the randomization strata may be removed. Forest plots will be

provided. Further subgroup analyses may be performed if deemed necessary for interpretation of results.

- Age group (<65, [65-75[and ≥ 75 years),
- Gender (male, female),
- Baseline BMI (<25, [25-30[, [30-40[and ≥ 40 kg/m²),
- Randomization stratum of screening HbA1c (<7.6%, $\geq 7.6\%$),
- Randomization stratum of site. (only if the size of subgroup is relevant)
- Duration of diabetes (<10, ≥ 10 years),
- Baseline estimated GFR categories (mL/min/1.73m²): (<60[; ≥ 60),

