2.1.4.1 Hypoglycemia events

All hypoglycemia will be categorized according to the ADA definitions (1) as described below:

- **Severe hypoglycemia:** Severe hypoglycemia will be derived as an event requiring assistance of another person to actively administer carbohydrate, glucagon, or other resuscitative actions.
- **Documented symptomatic hypoglycemia:** Documented symptomatic hypoglycemia will be derived as an event with symptoms of hypoglycemia and with a measured plasma glucose concentration less than or equal to 3.9 mmol/L (70 mg/dL).

- **Asymptomatic hypoglycemia:** Asymptomatic hypoglycemia will be derived as an event without symptoms of hypoglycemia but with a measured plasma glucose concentration less than or equal to 3.9 mmol/L (70 mg/dL).
- **Probable symptomatic hypoglycemia:** Probable symptomatic hypoglycemia will be derived as an event with symptoms of hypoglycemia and missing plasma glucose concentration.
- **Relative hypoglycemia:** Relative hypoglycemia (recently termed “pseudo-hypoglycemia”) will be derived as an event with symptoms of hypoglycemia but with a measured plasma glucose concentration greater than 3.9 mmol/L (70 mg/dL).

Hypoglycemia episodes will be analyzed regardless of the time of onset and in the following time periods defined by time of the day:

- Nocturnal hypoglycemia (defined by time of the day): any hypoglycemia that occurs between 00:00 and 05:59 a.m. hours, regardless whether patient was awake or woke up because of the event.
- Daytime hypoglycemia (defined by time of the day): any hypoglycemia that occurs between 6:00 a.m. to 23:59.
- Nocturnal hypoglycemia (defined by sleep status): any hypoglycemia waking the patient up from sleep after having gone to bed in the evening and before getting up in the morning (ie, before the morning determination of fasting pre-breakfast SMPG and before administration of insulin (IMP or NIMP)).

Some analyses will be also performed by distribution by hour of the day (0:00-23:59).

Hypoglycemia episodes will be analyzed only during the following period:

- 24-weeks TEAE period,

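### The SAP limits the ADA hypoglycemia categories to episodes with glucose ≤70 mg/dL and does not exempt severe events, which contradicts its own definition of severe hypoglycemia

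*SAP*

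**What the plan says.** SAP 2.4.5.1 plans two sets of descriptive results by ADA category. For incidence: "Number and incidence of patients with at least one hypoglycemia event will be presented for any hypoglycemia and for each hypoglycemia ADA category". The number of events and the rate per patient-year likewise "will be summarized for any hypoglycemia and for each hypoglycemia ADA category". A further summary concerns severe events only: "Percentage (%) of patients with at least one severe hypoglycemia event will be summarized by symptom during 24 weeks TEAE period". The section also says "Non classified hypoglycemia will be displayed". The between-group comparisons are planned for any hypoglycemia and "for each hypoglycemia ADA category (except probable, pseudo"), so severe events stay in the comparisons.

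The section then adds a restriction: "For Hypoglycemic ADA categories, only the threshold hypoglycemia episodes with plasma glucose ≤70 mg/dL (3.9 mmol/L) will be analyzed".

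The categories are defined in SAP 2.1.4.1. For severe events: "Severe hypoglycemia will be derived as an event requiring assistance of another person to actively administer carbohydrate, glucagon, or other resuscitative actions". For probable events: "Probable symptomatic hypoglycemia will be derived as an event with symptoms of hypoglycemia and missing plasma glucose concentration". Relative events have a measured value above 70 mg/dL. Documented symptomatic and asymptomatic events have a measured value at or below 70 mg/dL.

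Protocol 9.2.4.4.1 also defines severe events by need for assistance. It notes that a reading may be lacking and accepts neurological recovery after glucose is restored as sufficient evidence. The protocol synopsis (Safety analyses) and Protocol 11.4.3.4.1 plan to report severe events and set no glucose condition. SAP 1.5 and 1.6 declare no modification.

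**The concern.** The restriction covers the ADA categories as a group, but only two of the five have a reading at or below 70 mg/dL in their definition. Severe hypoglycemia has no glucose criterion at all. An assisted event with no reading, or with a reading above 70 mg/dL, meets the definition of severe and would then be left out of the analysis.

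Such events are foreseeable. Protocol 9.2.4.4.1 and 9.2.2.2.2 allow carbohydrate to be given before glucose is measured when safety requires it, and 9.2.4.4.1 then asks for a reading as soon as that is safe. The reading may therefore be missing, or taken after rescue.

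Severe hypoglycemia is a main safety outcome for insulin. Protocol 9.2.4.4.2 collects whether assistance was needed, so the data to classify these events exist. The same section keeps hypoglycemic events out of AE reporting unless they are serious. The hypoglycemia tables are therefore the main summary output for a non-serious severe event. The severe row of those tables could be too low and could disagree with other outputs from the same section.

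**Working it through.** The plan gives no figure to reproduce here; the check is one of wording.

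**Step 1. Apply the sentence to each category in SAP 2.1.4.1.**

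| Category | Glucose in the definition | Effect of the ≤70 mg/dL restriction |
|---|---|---|
| Severe | none (assistance only) | truncated |
| Documented symptomatic | ≤70 mg/dL | unchanged |
| Asymptomatic | ≤70 mg/dL | unchanged |
| Probable symptomatic | missing | emptied |
| Relative | >70 mg/dL | emptied |

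That is 1 truncated + 2 emptied + 2 unchanged = 5.

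**Step 2. Enumerate the combinations.** Cross assistance (yes, no), symptoms (yes, no) and glucose (missing, ≤70, >70): 2 × 2 × 3 = 12 cells. Assign severe first whenever assistance was needed; this order is an assumption. An event passes the restriction only if glucose is measured and ≤70 mg/dL.

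| Category | Cells | Kept as written | Kept if the cut-off applies only to documented symptomatic and asymptomatic |
|---|---|---|---|
| Severe | 6 | 2 | 6 |
| Documented symptomatic | 1 | 1 | 1 |
| Asymptomatic | 1 | 1 | 1 |
| Probable symptomatic | 1 | 0 | 1 |
| Relative | 1 | 0 | 1 |
| Not a hypoglycemia category | 2 | – | – |

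The severe result does not depend on the assumed order, since all six cells with assistance meet the severe definition in any case. The cells are logical combinations, not frequencies.

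**Step 3. Size.** Let m be the share of severe events without a reading ≤70 mg/dL. The documents do not give m. The fraction of severe events lost equals m: 0% at m = 0, 25% at m = 0.25, 50% at m = 0.5 and 100% at m = 1. With 15 randomized patients, one patient missing from the severe row is 1/15 = 6.7% of the total.

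**Step 4. Outputs affected.**

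- The synopsis plans three groupings: any, severe and documented symptomatic. Only severe can lose events, because any is not an ADA category and documented symptomatic already requires ≤70 mg/dL. That is 1 of 3.
- SAP 2.4.5.1 has three descriptive summaries that cover severe events. Incidence and rate are by ADA category and fall under the sentence (2 of 3). For the severe-by-symptom summary the SAP does not say whether the sentence applies, so one section could give two different counts of patients with severe hypoglycemia.

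**Step 5. Look for an exemption elsewhere.** The exception for probable and pseudo concerns the comparisons, not the descriptive results, and does not name severe. SAP 2.5.3 refers missing classification items to the ADaM metadata, which are not part of these documents. Glucose is not an item in the severe definition, and SAP 2.5.3 states no exemption from the restriction.

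**The case against.** The strongest reply is that the sentence was never meant as a filter. It speaks of threshold episodes, and the section promises results for every ADA category. Excepting probable and pseudo from the comparisons would also be pointless if both were already empty. Read as saying that 70 mg/dL is the only glucose cut-off in use, the sentence conflicts with nothing. That is probably the intent, but neither document states it, and a programmer who follows the text would apply a filter.

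Second, Protocol 9.2.4.4.1 speaks explicitly only of readings that are unavailable, not of readings above 70 mg/dL. This is fair. For a reading above 70 mg/dL the conflict follows from the assistance-only definition, not from an explicit statement.

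Third, the two emptied categories are a certain consequence of the literal reading, whereas severe may lose nothing. Protocol 11.4.3.4.1 and the SAP do plan results for every type of event. The emptied categories are therefore part of the error, although the synopsis limits incidence and rates to any, severe and documented symptomatic.

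Fourth, the practical effect is small. A removed event might still appear under any hypoglycemia, as non-classified, in listings, in SAE reporting if serious, or in the severe-by-symptom summary if the restriction is not applied there. Events with seizure, unconsciousness or coma must be reported as SAEs. The opening of SAP section 2 leaves only descriptive tables or listings for 15 patients. All of this stands. It limits the consequence but does not make the rule correct.

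**Conclusion.** The concern holds: the sentence is wrong as written. Followed literally, it truncates the severe category and empties the probable symptomatic and relative categories. That contradicts SAP 2.1.4.1, the results promised in SAP 2.4.5.1, and the protocol's definition and analysis of severe events. The conclusion rests on the literal text and on the absence of any stated exemption; the ADaM rule could not be seen.

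The number of severe events affected is unknown and may be zero, and nothing shows that the two groups would be affected differently. The consequence is limited to the descriptive output of a terminated study. The sentence should nevertheless be corrected, because in so small a sample one omitted severe event could change the safety summary.

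**What to change.** Replace the sentence in SAP 2.4.5.1 with:

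> The 70 mg/dL (3.9 mmol/L) threshold is the only glucose cut-off used and applies to documented symptomatic and asymptomatic hypoglycemia. Severe events are counted whatever the glucose value or its availability; probable symptomatic and relative events are counted as defined in 2.1.4.1.

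Then check that the ADaM classification rule cited in SAP 2.5.3 agrees, and that the severe-by-symptom summary uses the same set of severe events as the tables by ADA category. The cost is one SAP sentence and one check of the metadata. No new data or analyses are needed, and sample size, power and alpha are unaffected. The change concerns how events are counted, not how patients are managed.

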2.4.5.2 Analyses of adverse events

Generalities

The primary focus of adverse event reporting will be on treatment-emergent adverse events. Pre-treatment and post-treatment adverse events will be described separately.

If an adverse event date/time of onset (occurrence, worsening, or becoming serious) is incomplete, an imputation algorithm will be used to classify the adverse event as pretreatment, treatment-emergent, or post-treatment. The algorithm for imputing date/time of onset will be conservative and will classify an adverse event as treatment emergent unless there is definitive information to determine it is pretreatment or post-treatment. Details on classification of adverse events with missing or partial onset dates are provided in [Section 2.5.3](#).

Adverse event incidence tables will present by SOC, HLG, HLT, and PT, sorted in alphabetical order for each study conduct approach group, the number (n) and percentage (%) of patients experiencing an adverse event. Multiple occurrences of the same event in the same patient will be counted only once in the tables within a treatment phase. The denominator for computation of percentages is the safety population within each study conduct approach group.

Sorting within tables ensures the same presentation for the set of all adverse events within the observation period (pretreatment, treatment-emergent, and post-treatment). For that purpose, the table of all treatment-emergent adverse events presented by SOC and PT sorted by the internationally agreed SOC order and decreasing frequency of PTs within SOCs will define the presentation order for all other tables unless otherwise specified. Sorting will be based on results for the Virtual arm.

Analysis of all treatment-emergent adverse events

The following treatment-emergent adverse event summaries will be generated for the safety population.

- Overview of treatment-emergent adverse events, summarizing number (%) of patients with any
 - Treatment-emergent adverse event
 - Serious treatment-emergent adverse event

- Treatment-emergent adverse event leading to death
- Treatment-emergent adverse event leading to permanent treatment discontinuation
- All treatment-emergent adverse event by primary SOC, HLG, HLT, and PT, showing number (%) of patients with at least 1 treatment-emergent adverse event sorted by the SOC internationally agreed order. The other levels (HLG, HLT, PT) will be presented in alphabetical order.
- All treatment-emergent adverse events by primary SOC and PT, showing the number (%) of patients with at least 1 treatment-emergent adverse event, sorted by the internationally agreed SOC order and by decreasing incidence of PTs within each SOC. This sorting order will be applied to all other tables, unless otherwise specified.
- All common treatment-emergent adverse event (HLT incidence $\geq 2\%$ in any study conduct approach group) by primary SOC, HLT, and PT, showing number (%) of patients with at least 1 common treatment-emergent adverse event sorted by the SOC internationally agreed order. The other levels (HLT, PT) will be presented in alphabetical order.
- All treatment-emergent adverse events regardless of relationship and related to IMP by primary SOC, HLG, HLT and PT, showing the number (%) of patients with at least 1 treatment-emergent adverse event, sorted by the internationally agreed SOC order. The other levels (HLG, HLT, PT) will be presented in alphabetical order.
- All treatment-emergent adverse events by maximal severity, presented by primary SOC and PT, showing the number (%) of patients with at least 1 treatment-emergent adverse event by severity (ie, mild, moderate, or severe), sorted by the sorting order defined above.

Analysis of all treatment emergent serious adverse event(s)

- All treatment-emergent serious adverse events by primary SOC, HLG, HLT, and PT, showing the number (%) of patients with at least 1 serious treatment-emergent adverse event, sorted by the internationally agreed SOC order. The other levels (HLG, HLT, PT) will be presented in alphabetical order,
- All treatment-emergent serious adverse events regardless of relationship and related to IMP, by primary SOC, HLG, HLT, and PT, showing the number (%) of patients with at least 1 treatment-emergent serious adverse event, sorted by the internationally agreed SOC order. The other levels (HLG, HLT, PT) will be presented in alphabetical order.

Analysis of all treatment-emergent adverse event(s) leading to treatment discontinuation

- All treatment-emergent adverse events leading to treatment discontinuation, by primary SOC, HLG, HLT, and PT, showing the number (%) of patients sorted by the internationally agreed SOC order. The other levels (HLG, HLT, PT) will be presented in alphabetical order.

Analysis of injection site reactions and hypersensitivity reaction TEAE(s)

- All treatment-emergent adverse events related to injection site reactions or hypersensitivity reactions, by PT, showing the number (%) of patients sorted by decreasing incidence of PTs in Virtual arm.

Analysis of adverse events of special interest

- A listing of patients with symptomatic overdose with IMP/NIMP, pregnancy and unusual lack of efficacy of IMR (Canada only) will be provided separately.

Analysis of pretreatment and post-treatment adverse events

- All pre-treatment adverse events by primary SOC and PT, showing the number (%) of patients with at least 1 pre-treatment adverse event, sorted by the internationally agreed SOC order and decreasing incidence of PTs in Virtual arm within each SOC. (If more relevant a listing will be performed instead of table).
- All pre-treatment adverse events leading to study discontinuation by primary SOC and PT, showing the number (%) of patients, sorted by the internationally agreed SOC order and decreasing incidence of PTs Virtual arm within each SOC. (If more relevant a listing will be performed instead of table).
- All post-treatment adverse events by primary SOC and PT, showing the number (%) of patients with at least 1 post-treatment adverse event, sorted by the internationally agreed SOC order and decreasing incidence of PTs Virtual arm within each SOC.
- All post-treatment serious adverse events by primary SOC and PT, showing the number (%) of patients with at least 1 posttreatment serious adverse event, sorted by the internationally agreed SOC order and decreasing incidence of PTs Virtual arm within each SOC.
- Listing of SAE.
- Listing of AEs leading to permanent treatment discontinuation.

2.4.5.3 Deaths

The following summaries of deaths will be generated for the safety population.

- Number (%) of patients who died by study period (on-study, pre-study, on-treatment, post-study).
- Deaths in non-randomized patients or randomized but not treated patients.
- Treatment-emergent adverse events leading to death (death as an outcome on the adverse event case report form page as reported by the Investigator) by primary SOC, HLGT, HLT, and PT showing number (%) of patients sorted by internationally agreed SOC order, with HLGT, HLT, and PT presented in alphabetical order within each SOC.
- All pre-treatment adverse events leading to death by primary SOC and PT, showing the number (%) of patients, sorted by the internationally agreed SOC order and decreasing incidence of PTs within each SOC,
- All post-treatment adverse events leading to death by primary SOC and PT, showing the number (%) of patients, sorted by the internationally agreed SOC order and decreasing incidence of PTs within each SOC,
- Listing of deaths.

2.4.5.4 Analyses of laboratory variables

The summary statistics (including number, mean, median, standard deviation, minimum and maximum) of all laboratory variables (central laboratory values) will be calculated at baseline by study conduct approach group. This section will be organized by biological function as specified in [Section 2.1.4.4](#).

2.4.5.5 Analyses of vital sign variables

The summary statistics (including number, mean, median, standard deviation, minimum and maximum) of all vital signs variables blood pressure, heart rate and body weight (and changes from baseline) will be calculated for each visit or study assessment (baseline, each post baseline time point, last on-treatment) by study conduct approach group.

The incidence of PCSAs at any time during the treatment-emergent adverse event period will be summarized by study conduct approach group irrespective of the baseline level and/or according to the following baseline status categories:

- Normal/missing.
- Abnormal according to PCSA criterion or criteria.

The change in body weight from baseline to Week 24 will be analyzed in the safety population using a similar MMRM model as described in [Section 2.4.4.1.1](#).

2.4.5.6 Analyses of electrocardiogram variables

Not applicable

2.4.6 Analyses of pharmacokinetic and pharmacodynamic variables

Not applicable

2.4.7 Analyses of PRO and ClinRO variables

The analysis of the following endpoints will be conducted on the ITT population, on the 24-week randomized period, ie, using all available post-baseline data, regardless of IMP discontinuation.

No p-value will be provided.

For interpretation of results, Effect Sizes (ES) using Cohen's definition will be calculated in order to interpret changes from baseline to Week 24 in PRO scores.

- Within ES: calculated at the study conduct approach group level, when focusing on changes from baseline
- Between ES: Calculated when comparing study conduct approach groups

The calculation and interpretation of ES is described on [Section 2.5.1](#).

To help the interpretation of PROs and ClinRO, plots will be provided if relevant.

